3 PROTOCOL SUMMARY

3.1 SYNOPSIS

Title:	Self-Test Strategies and Linkage Incentives to Improve ART and PrEP Uptake in Men			
Grant Number:	1R01 MH120176			
Brief Summary:	This is a randomized controlled trial to test a combination behavioral and biomedical intervention to improve the HIV prevention and care cascades in a population of mobile men in a high priority setting (fishermen in Kenya). The intervention strategy is to recruit and train highly socially-connected men to distribute HIV self-tests and provide linkage support to men in their close social networks. The study will determine whether this social network-based approach along with small financial incentives in the form of transport vouchers and biomedical technologies can increase men's HIV testing (within3 months linkage to and uptake of ART and PrEP after testing (within 3 months, and virologic suppression (HIV RNA < 400 c/mL) at 6 months and PrEP adherence (tenofovir levels of >=1500 ng/mL in urine) at 6 months. The study includes a longitudinal qualitative and mixed methods quantitative and qualitative assessments to identify the pathways of intervention action, and understand how the social network-based approach with support for linkage affects testing and ART and PrEP uptake and retention in men.			
Study Design:	Cluster randomized controlled trial of a combination intervention to increase men's HIV testing uptake, increase their linkage to and uptake of ART and PrEP, and improve their outcomes (virologic suppression for HIV-infected men and adherence to PrEP in uninfected men)			
Study Population:	At least 650 and up to 1,800 men aged ≥18 years who are primarily working in the fishing industry or related activities, who reside in beach communities in Siaya. Study population will consist of up to 140 clusters of men with close social network ties with a variable number of men in each cluster.			
Description of Sites/Facilities Enrolling Participants:	 Clinic sites: up to 10 beach landing sites and associated clinics, within one or more sub-counties, Rarieda, Bondo and Alego Usonga, in Siaya County in western Kenya Community sites: up to 10 Lake Victoria beach communities (with Beach Management Unit -governed landing sites) within sublocations in Rarieda, Bondo and/or Alego Usonga 			

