Outcome Measures:	 Primary outcomes Self-reported HIV testing within 3 months of intervention start Linkage to care or prevention within 3 months of intervention start Viral suppression (HIV RNA <400 c/mL) at 6 and 12 months among HIV-positive participants PrEP adherence at 6 months Secondary outcomes Initiation of ART or PrEP within 3 months confirmatory test or PrEP eligibility screening Confirmatory HIV testing uptake 3 to 6 months after intervention start
	financial incentives to offset transport costs) to other men in their close social network.

Self-Test Strategies and Linkage Incentives to Improve ART and PrEP Uptake in MenVersion 11.0November 29, 2022

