8.3 SOCIAL NETWORK MAPPING

After the social network survey data collection is completed, data will be analyzed and the close social networks of participants will be identified. These close social networks, clusters, will then be randomized 1:1 to intervention and control groups. Network-central, highly socially-connected men ("promoters") will be identified in each network group (one per group, with additional 'adjacent' alternates identified if primary potential promoters do not consent to participate as promoters). The study team will contact the potential promoters to administer informed consent to participate in the study as promoters; recruitment will proceed until at least n=45 and up to n=70 men in intervention, and at least n=45 and up to n=70 in control groups have been enrolled as promoters.

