8.4 BASELINE SURVEY

Visit 2 for up to n=1000 individuals mapped in the social networks

Based on men who have agreed to be in the study and were mapped to social networks, and the close social network cluster randomized, we will conduct a baseline survey with all network members and their central promoters. This baseline survey will include socio-demographic, health and sexual behaviors, including HIV testing history and will serve as the baseline for a number of measures prior to the study implementation.

The baseline survey is included as an attachment to this protocol.

8.5 **PROMOTER TRAININGS**

Visit 3 for up to n=140 promoters from the study population of up to n=1000 men

All men who are enrolled/consent as promoters (i.e. in both study groups) will participate in mandatory core training sessions. For the intervention group, an enhanced training of up to two days will be facilitated by study personnel and trainers, and will orient them to the study, their role, as well as equip them with enhanced knowledge about HIVST, information about HIV, PrEP, and treatment, including learning about the benefits of HIV testing (materials are included as attachments to this protocol). Promoters will be trained in the usage of oral fluid-based HIV tests (Oraquick Advance, approved for use in Kenya and other countries), and in how to interpret the results of self-tests. Building on prior work of the investigative team, the study team will utilize instruction sheets (with pictures and local language text) that have been developed in the setting (Kenya) to explain self-test usage. The team will also train promoters on how to use motivational interviewing techniques to motivate others to use self-tests, and the importance of confidentiality as a part of the study. For the control group, a basic training will be provided to present the study, importance and benefit of HIV testing, care, and prevention. The training will also cover issues related to confidentiality.

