1.2 SAMPLE SIZE DETERMINATION AND POWER CALCULATIONS

Aim 1

We calculate that the study will have an 80% or greater power to detect a significant difference in the proportion of HIV testing associated with the intervention arm, assuming a proportion self-testing in the control arm of 38% (observed data from SEARCH in fishermen) if the proportion testing in the intervention arm is 52% or greater (odds ratio of 1.8), calculated using an Intraclass Correlation Coefficient (ICC) of 0.15 (conservative based on SEARCH data), 70 clusters each in the intervention and control arms, average cluster size of 7 in both arms, and a type-1 error rate of 5%.^{125,126} Figure 2 shows statistical power and the range of detectable odds ratios over extremes of clustering effects.

Aim 2

For the Aim 2 combined primary outcome of successful linkage to ART or PrEP within 3 months of intervention start (+about 1 month), this study will have a 80% or greater power to detect a significant increase in successful linkage, assuming a proportion successfully linked at 3 months in the control arm of 24% (based on observed SEARCH trial linkage rates weighted for the number of eligible PrEP HIV-negative men and HIV-positive men not currently in HIV care) if the observed proportion in the intervention arm is 39% or greater (odds ratio of 2.0), using an ICC of 0.15, 70 clusters each in intervention and control arms, a cluster size of 7 in both arms, and a type-1 error rate of 5%. Statistical power for combined ART or PrEP

start is similar, with a reduction in anticipated eligible numbers per cluster reduced to 6 resulting in a small increase in the detectable odds ratio to 2.2 or greater. Power for a separate analysis of ART initiation alone is likely to be low given the small numbers of new HIV infections in the study sample with odds ratios in excess of three or four required.

Aim 3

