#### 3) Protocol version

This SAP references Owete Protocol Version 4.0, last updated May 5, 2020.

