#### 11) Statistical Power:

**Aim 1:** We calculate that the study will have an 80% or greater power to detect a significant difference in the proportion of HIV self-testing associated with the intervention arm, assuming a proportion self-testing in the control arm of 38% (*observed data from SEARCH study in fishermen*) if the proportion testing in the intervention arm is 52% or greater (odds ratio of 1.8), calculated using an Intraclass Correlation Coefficient (ICC) of 0.15 (*conservative based on SEARCH data*), 40 clusters each in the intervention and control arms, average cluster size of 8 in both arms, and a type-1 error rate of 5%. Figure 2 shows statistical power and the range of detectable odds ratios over extremes of clustering effects.

**Aim 2:** For the Aim 2 combined primary outcome of successful linkage to ART or PrEP within 3 months of intervention start, defined as when the promotor receives the kits at the end of the promotor training which will be upon completion of the baseline survey for that beach. This study will have a 80% or greater power to detect a significant increase in successful linkage, assuming a proportion successfully linked at 3 months in the control arm of 24% (*based on observed SEARCH trial linkage rates weighted for the number of eligible PrEP HIV-negative men and HIV positive men not currently in HIV care*) if the observed proportion in the intervention arm is 39% or greater (odds ratio of 2.0), using an ICC of 0.15, 40 clusters each in intervention and control arms, a cluster size of 8 in both arms, and a type-1 error rate of 5%. Statistical power for combined ART or PrEP start is similar, with a reduction in anticipated eligible numbers per cluster reduced to 6 resulting in a small increase in the detectable odds ratio to 2.2 or greater. Power for a separate analysis of ART initiation alone is likely to be low given the small numbers of new HIV infections in the study sample with odds ratios in excess of 3 or 4 required.

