### Section 4: Statistical Principles

### 16) Level of statistical significance:

Standard levels of significance testing will be used (p=0.05) for two sided-tests. We will report 95% confidence intervals and exact p-values (or p<0.001).

**17)** Description and rationale for any adjustment for multiplicity: (if so, detailing how the type I error is to be controlled.) Our primary outcomes were established in our protocol, and thus no adjustments will be made for multiplicity.

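### SAP 11 states at least 80% power for Aim 1, but its own inputs give 70% under the SAP's two-sided 5% test; the current protocol's design gives 89%, and its recruitment floor 73%

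*SAP*

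**What the plan says.** **SAP 11, Aim 1.** Power is put at 80% or more for 38% in control against 52% in intervention (described as an odds ratio of 1.8), with an ICC of 0.15 and "40 clusters each in the intervention and control arms, average cluster size of 8 in both arms, and a type-1 error rate of 5" percent. That sentence does not say whether the test is one- or two-sided.

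**SAP 16.** "Standard levels of significance testing will be used (p=0.05) for two sided-tests". SAP 17 makes no multiplicity adjustment, so the full 5% is available to Aim 1.

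**SAP 3.** "This SAP references Owete Protocol Version 4.0, last updated May 5, 2020". The protocol supplied is a later one: its version line reads "ART and PrEP Uptake in MenVersion 11.0November 29, 2022".

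**Protocol 1.2, Aim 1.** The same 80% claim, proportions and ICC now rest on "70 clusters each in the intervention and control arms, average cluster size of 7 in both arms".

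**Protocol 8.3.** Promoters are identified one per network, and "recruitment will proceed until at least n=45 and up to n=70 men in intervention", with the same range for control.

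**Other network or promoter counts in the current protocol**
- Synopsis: "Study population will consist of up to 140 clusters of men with close social network ties".
- Section 8.5 (promoter trainings): "Visit 3 for up to n=140 promoters from the study population of up to n=1000 men".
- Section 8.9 (ongoing promoter support): up to 70 promoters in the intervention arm.
- Study rationale (4.1): 80 networks in total.
- Consent procedures (4.1.2, item 4): up to 45 promoters per arm, 90 in all.

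**The concern.** SAP 11 prints every input needed to recompute its power, and the stated figure does not follow from them under the test that SAP 16 specifies. A reader of SAP 11 takes the Aim 1 type II error as 20% at most, when for the design described there it is 30%.

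The current protocol has moved to a larger design that meets its claim. It also permits recruitment to end at 45 networks per arm, where the type II error is 27% at size 7. That matters for reading a null Aim 1 result if recruitment ends near the floor. The leftover lower counts add to the difficulty: a reader cannot tell from the protocol alone whether about 40, 45 or 70 networks per arm is intended.

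**Working it through.** **Inputs.** From SAP 11: p1 = 0.38, p2 = 0.52, ICC = 0.15, k = 40 networks per arm, m = 8 men per network. From SAP 16: two-sided α = 0.05. From Protocol 1.2: k = 70, m = 7. From Protocol 8.3: minimum k = 45, with one promoter per network. Protocol 1.2 gives no sidedness, so the two-sided rule is carried over from SAP 16.

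**Formulas**
- Design effect: DE = 1 + (m − 1) × ICC
- Effective n per arm: n = k × m / DE
- Power = Φ{[(p2 − p1) − z × SE0] / SE1}, where SE0 = √[2p̄(1 − p̄)/n], p̄ = (p1 + p2)/2 and SE1 = √{[p1(1 − p1) + p2(1 − p2)]/n}

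**The SAP's own figure, 40 × 8**
- DE = 1 + 7 × 0.15 = 2.05; n = 320/2.05 = 156.1
- p̄ = 0.45; SE0 = √(2 × 0.45 × 0.55/156.1) = 0.0563; SE1 = √[(0.2356 + 0.2496)/156.1] = 0.0557
- Two-sided (z = 1.960): (0.14 − 0.1104)/0.0557 = 0.53, so power = **70.2%**
- One-sided (z = 1.645): (0.14 − 0.0926)/0.0557 = 0.85, so power = 80.2%

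The stated 80% is therefore reproduced only by a one-sided test. Other two-sided methods do not rescue it: unpooled variance 70.9%, t with 78 degrees of freedom 69.9%, arcsine 70.4%, log-odds 69.8%. At an odds ratio of exactly 1.8 (p2 = 52.45%) power is 73.0%.

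**Comparison with the other aims in SAP 11, two-sided**
- Aim 2, 24% versus 39% on the same 40 × 8: 81.7%, which meets its claim.
- Aim 3, assuming the 168 + 72 = 240 men split equally, with the stated design effect of 1.7 (n = 120/1.7 = 70.6): 80.5% for 70% versus 89%, and 80.4% for 81% versus 96%.

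Only Aim 1 falls short.

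**The current protocol, two-sided, 38% versus 52%**

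| Networks per arm × size | DE | Effective n | Power | Intervention proportion giving about 80% |
|---|---|---|---|---|
| 40 × 8 (SAP) | 2.05 | 156.1 | 70.2% | 53.7% (OR 1.90) |
| 45 × 7 (floor) | 1.90 | 165.8 | 72.85% | 53.3% (OR 1.86) |
| 45 × 8 (floor) | 2.05 | 175.6 | 75.3% | not computed |
| 70 × 7 (planned) | 1.90 | 257.9 | 89.4% | 50.3% (OR 1.65) |

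**How far off**
- For 80% power at 52%, 54 networks per arm of 7 are needed (53 give 79.6%, 54 give 80.4%), or 51 of 8 (50 give 79.6%, 51 give 80.4%).
- 40 × 8 reaches 80% only if the ICC is 0.089 or less.
- Taking the synopsis minimum of 650 men and assuming all contribute: spread over 90 networks (7.2 each) power is 73.4%; over 140 networks (4.6 each) it is 82.5%. The shortfall at the floor comes from the number of networks, not the number of men.
- SAP 10 says networks typically hold 4 to 10 men. Assuming sizes uniform on that range (mean 7, CV 0.286) and DE = 1 + [(CV² + 1) × 7 − 1] × 0.15 = 1.99, power is 71% at 45 per arm and 88% at 70.

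**The case against.** **The design has been replaced.** The 40 × 8 design belongs to a SAP tied to an older protocol, and the current 70 × 7 design exceeds its claim. The error changes no sample size or analysis. This stands and limits the weight of the point. But the SAP supplied still carries the figure, and it is wrong for its own inputs.

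**A one-sided test may have been meant.** It reproduces the figure almost exactly. But it contradicts SAP 16, and Aims 2 and 3 in the same section meet their claims two-sided. The cause of the gap is not stated; under either reading the sentence needs correcting.

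**The effect is also given as an odds ratio of 1.8.** At exactly 1.8 the power is 73%, so the stated inputs support 70% to 73%. That is fair, and still at least 7 points short.

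**The floor is not a misstatement.** Nothing claims 80% at 45 per arm, and the protocol itself gives no sidedness (a one-sided test at 45 × 7 gives 82.3%). This stands: the floor is a missing disclosure, not an arithmetic error. Both documents also cite a figure on power across clustering effects, which is not available here. Its description does not suggest that it varies the number of networks.

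**The mismatched counts are a consistency matter.** Agreed. Several are ceilings (up to 70, up to 140), and only Protocol 1.2 states 70 per arm as a design value.

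**Changing the version citation alone would mislead.** Agreed. SAP content differs from Version 11.0 elsewhere: retention is assessed at 12 months in SAP 11 and 27, and at 6 months in Protocol 1.2 and 1.3.3.

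**Conclusion.** The concern holds. Under the SAP's two-sided 5% rule, Aim 1 power for 40 networks of 8 per arm is 70%, not 80% or more. The type II error is 30%, and the intervention proportion detectable with 80% power is 53.7% (odds ratio 1.90). At the current protocol's 70 × 7 the power is 89%, so its claim is met and the planned design is sound. At the recruitment floor of 45 × 7 it is 73%, which the text does not disclose.

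These figures assume the stated ICC of 0.15, equal network sizes and a normal approximation to the cluster-adjusted chi-square. Unequal sizes lower power slightly. Any dilution from counting missing outcomes as failure is not included, because no loss rate is given.

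This should be fixed, but it is a correction to the text and not a flaw in the planned trial.

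**What to change.** 1. In a SAP revision, restate SAP 11 Aim 1 on the current design with two-sided 5% and ICC 0.15: 70 networks per arm of 7 give 89% power for 38% versus 52%, or 80% for 38% versus 50.3%.
2. State power at the recruitment floor: 45 networks per arm of 7 give 73% for 52%, or 80% for 53.3%.
3. If the 40 × 8 calculation is kept for the record, give its power as 70% and name the test as two-sided.
4. Say which outcome the 38% and 52% describe. SAP 11 powers self-testing, Protocol 1.2 powers HIV testing while describing its 38% as self-testing, and SAP 26 lists both outcomes.
5. Update the protocol version in SAP 3 as part of that revision, after checking the rest of the SAP against Version 11.0.
6. In the protocol, reconcile the 80 networks in the study rationale (4.1) and the cap of 45 promoters per arm in the consent procedures (4.1.2, item 4) with the 70 per arm in section 1.2 and the ceilings of 70 per arm or 140 in total in the synopsis and sections 8.3, 8.5 and 8.9.

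The cost is text only. The stated power becomes less favourable at the lower network counts, and nothing in the planned 70 × 7 design changes.

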### 12) Framework

We will use the superiority hypothesis testing framework, testing whether exposure to the intervention results in better outcomes than exposure to the control standard of care. Comparisons will be presented as differences between arms in changes in outcomes during the study follow up period.

## 13) Statistical interim analyses and stopping guidance

- a. Information in interim analyses specifying what interim analyses will be carried out and listing time points
  - i. No interim analyses will be conducted.
- b. Any planned adjustment of the significance level due to interim analysis
  - i. Not applicable
- c. Details of guidelines for stopping the trial early
  - i. None

### 14) Timing of final analyses:

Analysis of baseline data will occur as beach communities are enrolled and will continue for one calendar year. Final analyses will begin immediately upon completion of all field data collection which is estimated to be completed within twelve months of freezing of the study database *c*.

### 15) Timing of outcome assessments:

Research staff will collect data from all study participants in both arms at approximately 0 months/baseline, 3 months, 6 months, and 12 months. All assessments will have a window of +/- 1 month. Outcome assessments collected via clinical chart abstraction (HIV confirmatory testing and results, PreP screening and uptake, and ART screening and regimen, clinic attendance), survey (self-reported testing), and via specimen collection and analysis (HIV viral load testing and PreP adherence) will be assessed within one month of each participant's 6 or 12 month outcome window, through a study-scheduled visit.

### Section 4: Statistical Principles

### 16) Level of statistical significance:

Standard levels of significance testing will be used (p=0.05) for two sided-tests. We will report 95% confidence intervals and exact p-values (or p<0.001).

**17)** Description and rationale for any adjustment for multiplicity: (if so, detailing how the type I error is to be controlled.) Our primary outcomes were established in our protocol, and thus no adjustments will be made for multiplicity.

### **18)** Confidence intervals:

95% confidence intervals will be reported alongside exact p-values.

### 19) Adherence and protocol deviations:

- a. Definition of exposure to the intervention and how this is assessed including extent of exposure:
  - ii. Exposure to the intervention will be measured in two independent parts:
    - 1. Being randomized to the intervention or control group. An individual's cluster will be randomized to either intervention or control group if they are part of a social network or designated as the promotor, or
    - 2. Receipt of the intervention (self-testing kit) from the social network promotor.
- b. Description of how adherence to the intervention will be presented consort diagram and brief description in the narrative

iii. Adherence to the intervention will be measured in the following ways:

	Table 1. Owele 5	tudy Huchty Wiedsur	CJ	
Intervention Component	Corresponding Study Aim	Fidelity Measure	Components	Time
Promotors training	Aim 1	Pre- and post- evaluation	Covers self- evaluation of knowledge of HIVST, confidentiality, and the roles of promotors	At beginning and end of promotor training
Promotors training	Aim 1	Pre- and post- evaluation	Promotor training attendance—sign in sheet	At training
Distribution of HIVST	Aim 2	Record of distribution by FRAs	Documentation of kits distributed by RAs to promotors which includes serial #s, expiry date, & distribution date.	At kit distribution date which should be last day of training.
Distribution of HIVST	Aim 2	Record of distribution by promotors	Self-reported list of fishermen the promotors gave kits to.	Collected by FRAs after all kits have been distributed during promotor follow up visit?
Receipt of HIVST	Aim 2	Record of receipt of HIVST from promotor	In 3 month survey. Need to add to survey to ask for name of promotor	During 3 month follow up
Usage of HIVST	Aim 2	Record of use of HIVST	In 3 month survey, will ask about use since baseline	During 3 month follow up
Engagement in Care	Aim 3	Linkage register – blue/green card extraction	Record (to validate self-reported clinic attendance)	During follow up visits
Receipt of HIVST, Engagement in Care	Aim 2-3	Receipt of transport voucher with unique ID	Transport voucher with unique network ID to give to clinic staff.	Attending confirmatory test visit

**Table 1: Owete Study Fidelity Measures** 

# c. Definition of protocol deviations for the trial

Protocol deviations are defined as any failure to achieve full exposure to the defined procedures or treatment plans outlined in the study protocol version previously approved by the IRB except if intended to eliminate a hazard to the study participant or protect the wellbeing or life of the study participant in an emergency. The noncompliance may be either on the part of the investigator or the study site staff and may result in significant added risk to the study subject. As a result of deviations, corrective and preventive actions are developed by the site and implemented promptly.

- d. Definition of which protocol deviations will be summarized:
  - i. Enrolling someone who doesn't meet the eligibility
  - ii. Study visits that fall outside the scheduled evaluation window (Anything outside of +/- 1 window would be a SERU issue)

